3. STUDY POPULATION

DESCRIPTION OF STUDY POPULATION: Participants enrolled in the Bronx and Brooklyn (former) WIHS (now MWCCS) sites, those who receive medical care from Einstein/Montefiore Medical Center, or other medical facilities will be invited to participate in the proposed research. Participants may also be recruited from provider referrals and word-of-mouth if eligibility can be confirmed. Specifically, 30 HIV-infected women on stable antiretroviral therapy and 30 uninfected women, who currently use cannabis will be recruited to participate in this study. The volunteers in these studies will be between 40 and 65 years old, non- pregnant females, who are medically and psychiatrically stable, competent to provide informed

consent, non-treatment-seeking, and have no/occasional (once weekly or less) substance use other than cannabis. Women will be tested for pregnancy at each visit. An HIV test will also be administered at the in-person screening visit to confirm the HIV status of those without a documented negative HIV test within the prior 12 months, or with unknown HIV status. Pre-test and post test counseling will be provided, and consent for testing will be obtained prior to administering an oral HIV test. Any participant with a new positive HIV test will be immediately linked to confirmation of test results and HIV care. None will have significant uncontrolled current Axis I psychopathology requiring medical intervention, or suicidal ideation or violent behavior within the past year. Participants with stable depression or anxiety on treatment will not be excluded from participation. Interviews in which drug use is probed will be conducted with each volunteer prior to study onset. Prospective volunteers expressing interest in stopping their cannabis use will be given a treatment referral. We expect to enroll approximately 60 volunteers over 2 years.

INCLUSION/EXCLUSION CRITERIA:

Inclusion criteria:

- 1. Adequate hearing and vision
- 2. Able to perform study procedures, including ability to ambulate independently
- 3. For HIV+ women: use of stable HAART for at least 6 months
- 4. Current cannabis use (within the past 6 months)

Exclusion criteria:

- 1. Illicit drug use other than cannabis more than once per week. Participants will be required to produce a negative urine drug test (other than cannabis) at each study visit.
- 2. Presence of significant uncontrolled medical illness: late stage or metastatic cancer or on active treatment for cancer; chronic pulmonary disease on ventilator or continuous oxygen therapy; uncontrolled hypertension (BP>160/100)
- 3. History of active heart disease within 12 months (e.g. myocardial infarction, unstable angina, heart failure, bypass surgery)
- 4. Interest in treatment for cannabis
- 5. Current parole or probation
- 6. Pregnancy or current lactation
- 7. Recent history of significant violent behavior (within 12 months)
- 8. Current uncontrolled Axis I psychopathology requiring medical intervention (e.g. active psychosis, suicide risk), or suicide attempt and/or suicidal ideation within 12 months
- 9. History of dementia
- 10. Severe hand tremor
- 11. Poor English fluency
- 12. Willingness to consent to HIV testing if status can not be confirmed from medical records

JUSTIFICATION FOR THE INCLUSION OF WOMEN ONLY, AND FOR THE EXCLUSION OF CHILDREN.

The former WIHS population is an ethnically diverse cohort of women with HIV infection as well as demographically and behaviorally similar uninfected controls and is representative of the domestic HIV epidemic in women. Based on characteristics of the MWCCS participants in our study sites, we anticipate that our sample will consist of: 53% Non-Hispanic black, 38% Hispanic, and 8% Non-Hispanic white/other. We have chosen to limit our proposal by sex in an effort to fill a critical gap of knowledge. Women represent a sizeable proportion of the growing number of older HIV-infected persons, yet they are often underrepresented in HIV research. Women represent 50% of all adults living with HIV globally, and account for 19% of all HIV diagnoses among U.S. adults. Because women have longer life spans than men, yet greater rates of geriatric outcomes such as frailty, falls, and disability, this innovative research on the effects of cannabis and HIV on the balance, mobility, and cognition among aging women is of particular importance as the greater numbers of HIV-infected women survive into old age. HIV- infected women have alarmingly high rates of geriatric syndromes such as falls and fractures, occurring at younger than expected age. Yet research incorporating sex-specific analyses is scarce and is limited in terms of the range of risk factors examined. With its robust dataset and specimens and over 20 years of follow-up, MWCCS is a unique and critical platform for investigations of disease in

HIV-infected women as they age, and in critically important studies of pathogenesis of comorbidities that disproportionately affect older women and intersect with substance use and HIV disease that are both broadly applicable and specific to women.

Participants included in this study will be women age 40 years or older, and the majority will be over age 50 years. Individuals under age 18 are specifically excluded, as well as adults below age 40, as the research topic to be studied is not relevant to children, or younger adults. This proposal aims to understand cannabis effects on balance, mobility, and cognition in aging HIV-infected women and uninfected controls, in an effort to understand potential mechanisms of fall risk and mobility impairment associated with HIV and cannabis use.

Sources of research material. Participants enrolled from MWCCS currently undergo annual research visits as a scheduled part of their MWCCS participation, which include in-depth interviews, physical exam, and collection of blood, oral, gynecologic, and urine specimens. MWCCS Core interviews include detailed evaluation of sociodemographics, medical and health history (HIV- and non-HIV related), medication use, HAART use, dosage and adherence, reproductive/gynecologic history, substance use, sexual behaviors, engagement in care, and brief pain inventory, among others. Medical exam consists of neuropathy exam, height, weight, anthropometry, bioelectric impedance analysis, blood pressure, and skin, oral cavity, breast, and gynecological examinations. A neurocognitive testing battery is performed in all participants every two years. For MWCCS participants who give medical record release, information will also be gathered from medical charts. Volunteers will be informed that data will be obtained specifically for research purposes. We will use as data all self-report information, observer records, and physiological, and behavioral information collected during test sessions, as well as data collected as part of MWCCS study visits. Electronic Health Records (EHR) will be used to screen participants recruited outside of MWCCS, i.e. clinical populations receiving care at Einstein/Montefiore, other medical facilities. Data will be coded with numbers assigned to each participant. Electronic transmission of information regarding a participant will only use an assigned number to identify the participant. Additionally, computers with participant-related information are password protected, and only study personnel have access to the passwords.

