STUDY SETTING The WIHS, established in 1994, was a prospective cohort study of HIV disease progression in women from 9 US cities, in which HIV+ and HIV- participants are well-matched by age, race/ethnicity, education, and high-risk sexual and substance use behavior. 86,87 Semi-annual visits included in-depth interviews, physical exam, and collection of blood, oral, gynecologic, and urine specimens. Current visit structure is now annual in MWCCS. Interviews include sociodemographics, medical history (HIV- and non-HIV related), medication use, HAART use and adherence, substance use, and report of falls and fall-related injury, among others. A neurocognitive testing battery is performed every two years. 88,89 MWCCS has a central Data Analysis and Coordination Center (DACC) and an extensive repository of biological specimens. The Cannabis Research Laboratory, Columbia University Medical Center (CUMC), is directed by [name]. Her laboratory has been conducting federally-funded, placebo-controlled human laboratory studies of cannabis administration for the past 20 years, including studies with HIV+ research volunteers. By collaborating with [name], we have the opportunity to directly assess the acute effects of active vs inactive cannabis administration on a range of clinically-relevant outcome measures, thereby dissociating expectancy effects of cannabis from its pharmacological effects.

STUDY PARTICIPANTS.

We will recruit and test 60 women who report cannabis use within the past six months, including 30 HIV+ women and 30 demographically similar HIV- controls from the Bronx and Brooklyn MWCCS sites, and from clinical populations, such as patients receiving care at Einstein/Montefiore Medical Center, other medical facilities, referred by medical providers, or word-of-mouth if eligibility can be confirmed. Median age of Bronx MWCCS participants is 54 years, with 75% between 49 and 59 years. Inclusion Criteria: (1) current cannabis use (within 6 months) based on self-report, (2) able to perform study procedures, including ability to ambulate independently, (3) adequate hearing and vision, (4) for HIV+ women, use of stable HAART for at least 6 months. Participants must be willing to smoke cannabis during both study

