visits. Participants who use cannabis by vaping but are willing to smoke cannabis at the study visits will be allowed to enroll. Exclusion criteria: (1) pregnancy, (2) greater than occasional illicit drug use other than cannabis will be excluded; those with weekly or less frequent substance use will be enrolled but will be require to provide a negative urine drug test (other than cannabis) at each of the two study visits, (3) request for substance use treatment, (4) current parole or probation, (5) history of significant violent behavior within 12 months, (6) current uncontrolled major Axis I psychopathology requiring medical intervention (e.g. active psychosis, suicide risk,), or suicide attempt and/or suicidal ideation within 12 months (7) significant uncontrolled medical illness (such as late stage or metastatic cancer or on active treatment for cancer; chronic pulmonary disease on ventilator or continuous oxygen therapy); uncontrolled hypertension BP>160/100), (8) active heart disease within 12 months, (9) history of dementia, (10) severe hand tremor, (11) poor English fluency. All participants will be consented and compensated for their effort as approved by the IRBs of each participating institution (see Human Subjects).

RECRUITMENT. Established MWCCS research infrastructure and clinical populations will be used for study recruitment. In order to meet recruitment targets, electronic health records will be used to prescreen for eligibility in clinical populations. We have obtained a waiver to access records for recruitment purposes. Potential participants will be contacted via phone to provide initial information about the study and screen for eligibility, followed by an in-person screening visit and initial consent. Written informed consent will then be obtained in person prior to study enrollment.

RANDOMIZATION AND BLINDING. Each participant will smoke both inactive (0.0%) and active (7.0%) cannabis; the order in which each cannabis strength is administered will be counterbalanced and double-blind. Participants will be told that the strength of cannabis that they will smoke in each session will vary.

RESEARCH VISITS AND STUDY PROCEDURES

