Those who pass this screening will have the study described to them in detail, and the study clinician will perform informed consent at that time. An oral HIV test will also be administered at the in-person screening visit to confirm the HIV status of those without a documented negative HIV test within the prior 12 months, those with unknown HIV status, or those without documented HIV positive status (either laboratory results, or medical records). Pre-test and post-test counseling will be provided, and informed consent for testing will be obtained prior to administering an oral HIV test. Any participant with a new positive HIV test will be immediately linked to HIV care. A copy of the signed consent form will be provided to the participant, as well as faxed to CUMC or uploaded into the study database and filed in a locked cabinet on site. A detailed questionnaire will be administered to participants recruited from clinical sources including sociodemographics, substance use history, medical and health history (HIV- and non-HIV related), and medication use including antiretroviral history and adherence.

Review of Study Procedures at Initial Study Visit. When they report to the laboratory for the initial study visit, participants will have additional study procedures described by [name].

We find that this multi-consent process provides participants with substantially more information at each decision point. Such a procedure provides fully informed consent.

Subject Renumeration

Compensation: We will pay subjects for their time and effort, \$50 for the screening visit and \$75 per each of two 4 hour study visit sessions. This modest amount is consistent with the compensation policies and guidelines approved by the institutional IRB.

Study Completion Bonuses: Participants who complete the entire study will be given a study completion bonus of \$50.

Participant Meals: Participants will receive a standardized low-fat breakfast (bagel, juice, coffee) at each study visit, and will also be provided with lunches and snacks on study visit days, consisting of frozen meals, snack foods, and beverages ordered in bulk or purchased from local supermarkets.

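### Exclusion criterion 12 on HIV testing is worded backwards, and Section 3 leaves eligibility above age 65 unresolved

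*Combined protocol and SAP*

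**What the plan says.** Section 3 ends its exclusion list with item 12: "Willingness to consent to HIV testing if status can not be confirmed from medical records". The other eleven items each name a reason to keep a woman out. The shorter list in Section 2 has no HIV-testing item; its exclusions stop at "11) poor English fluency".

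The testing procedure appears in three places. The population description in Section 3 and the consent process in Section 5 both provide for an HIV test at the in-person screening visit, in the words of Section 5 "to confirm the HIV status of those without a documented negative HIV test within the prior 12 months", and for women of unknown status. Section 5 adds women whose positive status is undocumented. Both sections require consent before the test. Section 4 adds that records of women from outside the cohort are reviewed for HIV status, with testing where documentation is missing.

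Age appears only in the prose of Section 3. The population description says "The volunteers in these studies will be between 40 and 65 years old". The later paragraph on the exclusion of children says "Participants included in this study will be women age 40 years or older" and, in the next sentence, "Individuals under age 18 are specifically excluded, as well as adults below age 40".

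**The concern.** Eligibility lists are what screeners and monitors work from. Section 5 makes meeting the inclusion and exclusion criteria the condition for being scheduled for the in-person visit, which is where the HIV test is done. Item 12 is therefore a working rule, and as written it conflicts with the procedure that follows it. Recruitment also extends beyond the cohort to clinic patients, provider referrals and word of mouth, where HIV documentation is more likely to be incomplete.

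At stake is consistent screening. A woman who agrees to the test is ineligible under item 12 and eligible under Sections 3 to 5, so either decision about her could be recorded as a protocol deviation. The same holds for a woman over 65, who fails one age statement in Section 3 and satisfies the other. HIV status is the between-group factor in both aims and the aims concern older women, so both rules help to define the comparison.

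**Working it through.** No arithmetic beyond counting applies, so the check is a side-by-side reading.

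**Item 12 against the testing procedure**

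| Woman | Item 12 read literally | Sections 3, 4 and 5 |
|---|---|---|
| HIV status confirmed from records | Not triggered | No documentation gap to resolve |
| Not confirmed, agrees to testing | Excluded | Tested at screening; status established |
| Not confirmed, refuses testing | Not excluded by this item | Cannot be tested, since consent is required first; status stays undocumented |

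The second and third rows are reversed. The second is the direct harm: the item removes the women for whom the screening test was provided. In the third row, the procedure sections do not say expressly what happens to a woman who declines. Item 12 is the only numbered criterion that addresses HIV testing, and it points the wrong way.

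**Who would be turned away.** HIV-positive entrants need stable treatment: "4) for HIV+ women, use of stable HAART for at least 6 months". A woman on such treatment would normally have records showing her status. By inference, the women caught by item 12 would mostly be candidates for the 30 HIV-negative places. The documents do not say how many recruits lack confirmation.

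**Age in the numbered lists**

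- Section 3: 4 inclusion + 12 exclusion = 16 items; 0 state an age.
- Section 2: 4 inclusion + 11 exclusion = 15 items; 0 state an age.

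**Age in the prose of Section 3**

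| Age | Population description | Paragraph on exclusion of children |
|---|---|---|
| Under 40 | Outside the range | Expressly excluded |
| 40 to 65 | Eligible | Eligible |
| Over 65 | Outside the range | Within the wording; no upper limit given |

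Only the last row conflicts. For scale, Section 2 puts 75% of Bronx cohort participants between 49 and 59, so at most 100% − 75% = 25% are older than 59, and those over 65 are some part of that. No age figures are given for the Brooklyn site or for clinic recruits, so the number affected cannot be derived.

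**The case against.** The strongest reply is that both points are drafting slips that the rest of the protocol neutralises. Sections 3, 4 and 5 make the intent of item 12 plain, and staff who know the procedure would probably read it correctly. On age, a sample aged 40 to 65 satisfies both statements. The second statement occurs where the exclusion of children and younger adults is justified, and it is silent on an upper bound rather than expressly admitting women over 65. No text says that the numbered lists override the prose. All of this is fair and limits the weight of the point. It does not make item 12 correct or state the upper age limit consistently.

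A reader might go further and infer that the list would let in women of untested status, mislabel the HIV groups and pull the HIV-by-cannabis interaction towards zero. The documents do not support that. Testing or documentation is required elsewhere, and referral and word-of-mouth recruits enter only if eligibility can be confirmed. A woman of unknown status cannot readily be placed in either group, and entry as HIV-positive also needs six months of stable treatment. Mislabelling would require a woman who refused testing to be recorded as HIV-negative while in fact infected. If a fraction m of one group were misclassified, the expected interaction would shrink by a factor (1 − m), but the documents give no value of m.

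A reader might also infer that, without an age item, women under 40 could be enrolled. The prose rules that out expressly.

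**Conclusion.** The point holds as an error in the eligibility rules, not as a demonstrated source of bias. Item 12 is inverted: its literal effect is to exclude consenting women whose status the screening test would establish, contrary to Sections 3, 4 and 5. The lower age limit of 40 is consistent, and only eligibility above 65 is open. Neither point changes the planned 60 women, the analysis or the stated detectable effects. The size of either problem depends on how many candidates lack HIV documentation or are over 65, and neither count is given. The conclusion assumes that the numbered list is applied as written; where staff follow the procedural sections instead, the practical effect of item 12 is small.

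**What to change.** 1. Move item 12 to the Section 3 inclusion list as a requirement, or keep it as an exclusion reworded along the lines of *unwilling to consent to HIV testing if status cannot be confirmed*. Either version also settles what happens to a woman who declines.
2. Have the investigators decide whether women over 65 are eligible, and make the two prose statements in Section 3 give the same range.
3. State that range as one numbered criterion in both the Section 2 and the Section 3 lists.

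The cost is a short protocol amendment and a matching change to any screening form built from the list. It adds no visits, tests or participants, and the analysis is unchanged.

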4. PARTICIPANT RECRUITMENT

Participants already enrolled in the Bronx and Brooklyn MWCCS sites and participants recruited from clinical care at Einstein/Montefiore Medical Center, or other medical facilities will be invited to participate in the proposed research. Specifically, 30 HIV-infected women on stable antiretroviral therapy and 30 uninfected women, who currently use cannabis will be recruited to participate in this study. Established MWCCS research infrastructure will be used for study recruitment. Potential participants will be contacted via phone to provide initial information about the study and prescreen for eligibility. Interested and potentially eligible participants will then complete an in-person screening visit at the Bronx MWCCS site, where written informed consent will be obtained prior to study enrollment. Clinical populations who meet eligibility requirements will also be eligible for participation. For Einstein/Montefiore patients, MWCCS personnel or a Center for AIDS Research (CFAR) nurse will utilize Einstein's CFAR clinical database to prescreen the electronic Health record for potential eligibility. Additionally, patients may be referred to the study by medical providers or word-of-mouth. Similar to the procedures for MWCCS participants, potential participants from clinical sources will be contacted via phone to provide initial information about the study, and will be prescreened for eligibility. Health records will be obtained and reviewed for non-MWCCS participants to ensure eligibility criteria are met, including documentation of HIV status. Interested and potentially eligible participants will then complete an initial telephone prescreen and an in-person screening visit at the Bronx MWCCS site, where written informed consent will be obtained and HIV testing will be performed if documentation of HIV status is unavailable.

5. INFORMED CONSENT

Obtaining informed consent is a multi-tiered process.

(1) Review of WIHS/MWCCS database The first phase of recruitment involves review of data collected as part of MWCCS core visits, to identify potential participants. For clinical populations, we will review Electronic Health Record (EHR) data obtained as part of clinical care to identify potential participants.

- (2) Telephone screening. Those deemed eligible based on this initial screening will receive phone calls from MWCCS study staff, receive a brief description of the study, and are asked to consent to be more fully screened via telephone. This screening consent form covers all interviews, questionnaires, and collection of medical information.
- (3) In-person medical and psychiatric evaluation and informed consent. Participants who meet inclusion/exclusion criteria will be scheduled for an in-person screening visit at the Bronx MWCCS site, which will include a physical exam, ECG, and medical and psychiatric history evaluation. Clinicians will determine whether volunteers have current untreated or uncontrolled major Axis I psychopathology requiring medical intervention (e.g., active psychosis, suicide risk,) or suicidal ideation or violent behavior within the past year. Psychiatric illness will be assessed using the Mini-International Neuropsychiatric Interview (M.I.N.I.), a short structured diagnostic interview, developed jointly by psychiatrists and clinicians in the United States and Europe. With an administration time of approximately 15 minutes, it was designed to meet the need for a short but accurate structured psychiatric interview for multicenter clinical trials and epidemiology studies and to be used as a first step in outcome tracking in non-research clinical settings. The M.I.N.I. was designed as a brief structured interview for the major psychiatric disorders in DSM-5 and ICD-10. Validation and reliability studies have been done comparing the M.I.N.I. to the SCID-P for DSM-III-R and the CIDI (a structured interview developed by the World Health Organization). The results of these studies show that the M.I.N.I. has similar reliability and validity properties, but can be administered in a much shorter period of time (median 15 minutes) than the above referenced instruments.

Those who pass this screening will have the study described to them in detail, and the study clinician will perform informed consent at that time. An oral HIV test will also be administered at the in-person screening visit to confirm the HIV status of those without a documented negative HIV test within the prior 12 months, those with unknown HIV status, or those without documented HIV positive status (either laboratory results, or medical records). Pre-test and post-test counseling will be provided, and informed consent for testing will be obtained prior to administering an oral HIV test. Any participant with a new positive HIV test will be immediately linked to HIV care. A copy of the signed consent form will be provided to the participant, as well as faxed to CUMC or uploaded into the study database and filed in a locked cabinet on site. A detailed questionnaire will be administered to participants recruited from clinical sources including sociodemographics, substance use history, medical and health history (HIV- and non-HIV related), and medication use including antiretroviral history and adherence.

Review of Study Procedures at Initial Study Visit. When they report to the laboratory for the initial study visit, participants will have additional study procedures described by [name].

We find that this multi-consent process provides participants with substantially more information at each decision point. Such a procedure provides fully informed consent.

Subject Renumeration

Compensation: We will pay subjects for their time and effort, \$50 for the screening visit and \$75 per each of two 4 hour study visit sessions. This modest amount is consistent with the compensation policies and guidelines approved by the institutional IRB.

Study Completion Bonuses: Participants who complete the entire study will be given a study completion bonus of \$50.

Participant Meals: Participants will receive a standardized low-fat breakfast (bagel, juice, coffee) at each study visit, and will also be provided with lunches and snacks on study visit days, consisting of frozen meals, snack foods, and beverages ordered in bulk or purchased from local supermarkets.

Transportation: For the screening visit, we will pay for round-trip taxi \$100 for Brooklyn participants to travel to the Bronx MWCCS; we will pay \$6.00 for one-way cost of public transportation for Bronx MWCCS participants. For study visits, we will pay for round-trip taxi \$160 per visit for travel expenses that include the significant costs of crossing NYC bridges to get to the Columbia University Medical

Center from the Brooklyn MWCCS site (N=20 per year). We will pay \$60 for one-way taxi for Bronx MWCCS participants, as well as \$6.00 for one-way cost of public transportation (N=40 per year). Transportation costs will be paid directly to the taxi service, and MetroCards will be given directly to participants.

